10.6.6 Hepatic Monitoring

If a participant experiences elevated laboratory parameters, as detailed in Section 8.2.8 of the protocol, additional tests will be performed to confirm the abnormality. Additional safety data may be collected if required, as defined in the protocol. Where applicable, the following will be presented.

The participants' liver disease history and associated person liver disease history data will be listed. Use of acetaminophen during the study, which has potential for hepatotoxicity, will be listed. Results from any hepatic monitoring procedures, such as a magnetic resonance elastography (MRE) scan, and biopsy assessments will be listed, if performed.

Hepatic risk factor assessment data will be listed. Liver related signs and symptoms data will be summarized by part and treatment, if deemed appropriate, and listed. Alcohol and recreational drug use data will also be listed.

All hepatic chemistry, hematology, coagulation, and serology data will be listed. Values outside the reference ranges will be flagged on the individual participant data listings.

10.6.7 Immunogenicity Assessments

Upon full assay validation, treatment-emergent antidrug antibodies (TE ADAs) may be assessed in line with Protocol section 9.3.4.4.

The relationship between the presence of antibodies and PK parameters of LY3872386 may be assessed if deemed appropriate.

10.6.8 Immunological status assessments

The WBC subpopulations (including, but not limited to, total B cells, total T cells, and NK cells), will be evaluated.

These data will be summarized by part, treatment, and time point, and listed. Changes from baseline will also be presented, where baseline is defined as the Day 1 predose assessment.

CONFIDENTIAL Protocol Reference: J4L-MC-KMAA

10.6.9 Hypersensitivity reactions

For all drug hypersensitivity reactions that occur, additional follow-up data will be collected to assess the participant's medical history, alternative causes, and symptoms.

These data will be listed.

10.6.14 Other assessments

All other safety assessments not detailed in this section will be listed but not summarized or statistically analyzed.

10.6.15 Safety and Tolerability Statistical Methodology

No inferential statistical analyses are planned.

10.7 Efficacy Assessment (Part B only)

10.7.1 Efficacy analysis

Efficacy analyses will be conducted on the mITT population. The exploratory efficacy analyses will estimate the effect of the treatment on the exploratory endpoints.

Clinician-rated scales:

Validated Investigator's Global Assessment for Atopic Dermatitis (vIGA-AD)

The vIGA-AD measures the investigator's global assessment of the participant's overall severity of their AD, based on a static, numeric 5-point scale from 0 (clear skin) to 4 (severe disease). The score is based on an overall assessment of the degree of erythema, papulation/induration, oozing/crusting, and lichenification.

Eczema Area and Severity Index (EASI)

The EASI assesses 4 clinical signs of disease, each on a 0 to 3 scale: (1) erythema, (2) induration/papulation, (3) excoriation, and (4) lichenification. Scores range from 0 to 72. The EASI evaluates 2 dimensions of AD: disease extent and clinical signs. Body surface area affected by AD will be derived from data collected as part of the EASI assessment.

SCORing Atopic Dermatitis (SCORAD)

The SCORAD index assesses: 1) 6 clinical signs of disease, each on a 0 to 3 scale, 2) the extent of involved surface area, up to 100%, and 3) subjective evaluations of itch and sleeplessness, each on a 0 to 10 scale. Scores range from 0 to 103.

Participant-rated scales:

Dermatology Life Quality Index (DLQI)

The DLQI is a 10-item questionnaire that covers 6 domains, including symptoms and feelings, daily activities, leisure, work and school, personal relationships, and treatment. The recall period for this scale is over the "last week." Response categories include "a little," "a lot," and "very much," with corresponding scores of 1, 2, and 3, respectively, and "not at all" or unanswered ("not relevant") responses scored as 0. Scores range from 0 to 30, with higher scores indicating greater impairment of quality of life. A DLQI total score of 0 or 1 is considered to indicate no effect on a participant's health-related quality of life, and a 4-point change from baseline is considered the minimal clinically important difference threshold.

Itch Numeric Rating Scale (NRS)

The Itch Numeric Rating Scale is a patient-administered, 11-point horizontal scale anchored at 0 and 10, with 0 representing "no itch" and 10 representing "worst itch imaginable." Overall

CONFIDENTIAL

Protocol Reference: J4L-MC-KMAA

CONFIDENTIAL Protocol Reference: J4L-MC-KMAA

severity of a patient's itching is indicated by selecting the number that best describes the worst level of itching in the past 24 hours.

Patient-Oriented Eczema Measure (POEM)

The Patient-Oriented Eczema Measure assesses the frequency of 7 symptoms (itching, sleep disturbance, bleeding, weeping/oozing, cracking, flaking, and dryness/roughness) over the last week. Response categories include "No days," "1 to 2 days," "3 to 4 days," "5 to 6 days," and "Every day," with corresponding scores of 0, 1, 2, 3, and 4, respectively. Scores range from 0 to 28, with higher total scores indicating greater disease severity.

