14.2 Missing Data

Missing data will not be displayed in listings.

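### The DLQI scoring rule gives an unanswered item the best score, 0, so skipped items can appear as change in quality of life, in either direction.

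*SAP*

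**What the plan says.** SAP 10.7.1 describes the scale and its scoring in one paragraph.

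- Structure: "The DLQI is a 10-item questionnaire that covers 6 domains".
- Answered items: "Response categories include 'a little,' 'a lot,' and 'very much,' with corresponding scores of 1, 2, and 3, respectively".
- Remaining items: 'not at all' and unanswered items share one value, in the words "unanswered ('not relevant') responses scored as 0".
- Direction: "Scores range from 0 to 30, with higher scores indicating greater impairment of quality of life".
- Low totals: 0 and 1 are both taken to mean that the patient's quality of life is unaffected.
- Threshold for change: "a 4-point change from baseline is considered the minimal clinically important difference threshold".

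The paragraph sets no maximum number of unanswered items and no condition under which the total becomes missing. Protocol 9.3.1 leaves the handling of missing data to the SAP. The SAP's own section on the subject, 14.2, reads in full "Missing data will not be displayed in listings", which concerns display and not scoring. DLQI is collected repeatedly in both Part B schedules (Protocol 1.3.2.1 and 1.3.2.2). Efficacy analyses are exploratory, use the mITT population and involve no hypothesis tests (Protocol 9.3.4.1).

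**The concern.** Marking an item 'not relevant' is a response, and a score of 0 for it is reasonable. Leaving an item blank is the absence of a response. The SAP sentence treats the two as the same thing and gives both the score for no impairment. Any blank therefore pulls that visit's total towards better health, whatever the patient's actual state. Change from baseline is distorted whenever the blanks differ between the two visits.

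What is at stake is the reliability of the DLQI summaries in Part B. Protocol 9.3.1 plans no significance tests because the groups are small, so readers will rely on descriptive values, and in small groups a single incomplete form carries noticeable weight.

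**Working it through.** **Inputs, all from SAP 10.7.1:** 10 items; item scores 0 to 3; unanswered = 0; higher total = worse; 4-point minimal clinically important difference.

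**Stated range.** Total = sum of the 10 item scores. Minimum 10 × 0 = 0 and maximum 10 × 3 = 30, which matches the SAP's range of 0 to 30.

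**Effect of skipped items when nothing has truly changed.** Let the skipped items have true scores x₁, …, x_k. If they are skipped after baseline, the change is −(x₁ + … + x_k). If they are skipped at baseline and answered later, the change is +(x₁ + … + x_k).

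| Items skipped (k) | Shift if each is 1 | Shift if each is 2 | Shift if each is 3 | Highest attainable total, 3 × (10 − k) |
|---|---|---|---|---|
| 1 | 1 | 2 | 3 | 27 |
| 2 | 2 | 4 | 6 | 24 |
| 3 | 3 | 6 | 9 | 21 |
| 4 | 4 | 8 | 12 | 18 |
| 5 | 5 | 10 | 15 | 15 |

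One skipped item shifts the total by at most 3 points, below the 4-point threshold. Two items at level 2 or 3 shift it by 4 to 6 points and reach the threshold, as do four items at level 1.

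**Worked example (assumed item scores).** Baseline items 2, 2, 2, 1, 1, 1, 1, 1, 1, 0 give a total of 12. With no true change:

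- First item skipped later: the SAP rule gives 10 (change −2). Prorating the nine answered items gives 10 × 10/9 = 11.1 (change −0.9).
- First two items skipped later: the SAP rule gives 8 (change −4).
- The same two items skipped at baseline and answered later: 8 rises to 12 (change +4).

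**Chance of a spurious 4-point fall, given k items skipped after baseline.** Assume independent items, each Binomial(3, p) with p = baseline total/30, and identical true answers at both visits. The sum of the skipped items is then Binomial(3k, p), and the chance is P(sum ≥ 4).

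- Baseline 15 (p = 0.5), k = 1: 0%, since the sum cannot exceed 3.
- Baseline 15, k = 2: (15 + 6 + 1)/64 = 34%.
- Baseline 15, k = 3: 1 − (1 + 9 + 36 + 84)/512 = 75%.
- Baseline 15, k = 5: 1 − (1 + 15 + 105 + 455)/32768 = 98%.
- Baseline 10 (p = 1/3), k = 3: 35%.
- Baseline 20 (p = 2/3), k = 2: 68%.

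These percentages are conditional on k. They do not say how often items would be skipped.

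**Effect on an arm mean.** The arm size is not visible. With an assumed 8 patients per arm, one form with a spurious shift of 4 points moves the arm's mean change by 4/8 = 0.5 points.

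**The case against.** The strongest reply is about reading. The sentence sits in a description of the instrument, among the response categories, and the parenthesis may mean only that the category 'not relevant' scores 0. That is a fair account of the likely intent. It does not settle the matter: the text says unanswered, and on the narrower reading a truly skipped item has no rule at all. The wording needs correcting either way.

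Three stronger inferences are tempting, and the documents do not support them.

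- That the rule turns missing answers into benefit. It does so only when the blank falls after baseline on an item that scored above 0. A blank at baseline works in the opposite direction, and the same rule applies to placebo patients.
- That a wholly blank form would be reported as no effect on quality of life. Ten zeros do sum to 0, inside the 0-to-1 band, but nothing says that an uncompleted form would be entered and totalled.
- That false DLQI responders would be counted. The SAP states the 4-point threshold, but no visible text uses it to define a responder. The descriptive part of SAP 10.7.2 and the name of the ANCOVA variable are not visible, so such an analysis can be neither confirmed nor excluded.

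Two further replies stand. The skip rate is unknown and could be low, since the investigator must confirm that CRF entries are complete (Protocol 10.1.7). No visible decision rests on DLQI: safety and tolerability are the primary criteria for dose escalation (Protocol 6.6.1).

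**Conclusion.** The point holds as a defect in a stated scoring rule, of low priority. Taken literally, the rule gives a skipped item the best-health score, and nothing in the visible text corrects or limits it. Two skipped items at level 2 or 3 are enough to reach the SAP's own 4-point threshold with no true change, as apparent improvement or worsening depending on which visit has the blanks. That result needs only the SAP's scoring figures. The percentages rest in addition on assumed baseline totals, independent items and a given number of blanks; the arm-mean figure rests on an assumed 8 patients. The frequency of the problem cannot be estimated from the documents. The consequence is limited to the exploratory DLQI summaries in Part B.

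**What to change.** In SAP 10.7.1:

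- Score an item 0 only when 'not at all' or 'not relevant' is actually selected.
- Treat a truly unanswered item as missing.
- Set the DLQI total to missing when two or more items are unanswered, which also covers a blank form.
- State how a single unanswered item is handled, for example by prorating: sum of the nine answered items × 10/9.

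The documents give no cut-off. Two is proposed because it is the smallest number of blanks at which zero-scoring alone can reach 4 points.

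The cost is a sentence or two in the SAP and a small change to the scoring program. The case report form must be able to record 'not relevant' separately from a blank; its layout is not visible. The downside is that a few incomplete forms give no total.

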10.7.2 Efficacy Statistical Methodology

Descriptive statistics

CONFIDENTIAL
Protocol Reference: J4L-MC-KMAA

Analysis of covariance (ANCOVA)

The mean percent change from baseline CCl data will be analyzed on Weeks 1 and 12 by an ANCOVA model with baseline as a covariate and treatment as a fixed effect to estimate the LS means and corresponding 90% CIs.

Example SAS code for the ANCOVA:

proc mixed data=saf1 method=reml;
 by param1;
 class treatment;
 model change = base treatment / residual cl alpha=0.1 ddfm=kr2;
 lsmeans treatment / alpha=0.1 cl pdiff;
 ods output lsmeans=lsmeans1 diffs=diff;
run;

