Amendment a	16-October 2023						
Original Protocol	01-September-2023						

Amendment: b

This amendment is considered to be nonsubstantial.

Overall Rationale for the Amendment:

This protocol has been amended to primarily address the FDA clinical non-hold comments regarding ophthalmological examinations, blood glucose monitoring, and treatment stopping criteria.

Minor editorial changes have also been made and are not presented in the summary of changes table.

Section # and Name	Description of Change	Brief Rationale				
Section 1.3.1: Part A: Single-Ascending Dose of LY3872386 in Healthy Participants	Added line item for bedside glucose monitoring to include time points on Day -1, Day 1, Day 2, and Day 7.	Updated to address FDA comments.				
	Added line item for hemoglobin A1c to include time points at screening, Day - 1, Day $29 \pm 1d$, Day $85 \pm 3d$, and ED.	Updated to address FDA comments and support additional treatment discontinuation and interruption criteria.				
	Added an ocular pressure, visual acuity, and cataract evaluation time point to Day $15 \pm 1d$ and $43 \pm 1d$. Provided additional to indicate that for follow-up Visit 802 and Visit 805, an ocular pressure assessment is required; additional visual acuity assessment may be conducted.	Updated to address FDA comments.				
Section 1.3.2: Part B: Multiple-Ascending Dose of LY3872386 in Patients with Atopic Dermatitis	Schedule: Added line item for hemoglobin A1c to include time points at screening, Day 1, Day 29 ± 1d, Day 85 ± 1d, Day 183 ± 3d, and ED.	Updated to address FDA comments and support additional treatment discontinuation and interruption criteria.				

Section # and Name	Description of Change	Brief Rationale					
	Added an ocular pressure, visual acuity, and cataract evaluation time point to Day $29 \pm 1d$, Day $57 \pm 1d$, and Day $88 \pm 1d$. Provided additional notes to state that for Visit 4, Visit 6, and follow-up Visit 801, an ocular pressure assessment is required; additional visual acuity and cataract assessment may be conducted.	Updated to address FDA comments.					
	Schedule: Added line item for hemoglobin A1c to include time points at screening, Day 1, Day $29 \pm 1d$, Day $85 \pm 1d$, Day $183 \pm 3d$, and ED.	Updated to address FDA comments and support additional treatment discontinuation and interruption criteria.					

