1.3.2. Part B: Multiple-Ascending Dose of LY3872386 in Patients with Atopic Dermatitis

1.3.2.1. Part B: LY3872386 CC Dosing Schedule

1.3.2.1. Part B	5: LY38/23	00 CC		D. 4 D. I		osing S				1 .				
Procedures/ Assessments	Screening		 	Part B: I Treat	ment Po			Do	osing Sch	Follo	w-up		ED	Comments
Visit Number	V1	V2	V3	V4	V5	V6	V7	V8	V 801	V 802	V 803	V 804		
Study Day(s)	CC													
Informed consent	X													
Review/confirm I/E criteria	X	P												
IWRS randomization		P												
Clinical Assessments														
Complete medical history	X													
Review preexisting conditions/AEs	X	P	P	P	P	P	P	P	X	X	X	X	X	
Concomitant medications	X	P	P	P	P	P	P	P	X	X	X	X	X	
Previous and current AD treatments	X													
Substance use (alcohol and tobacco use)	X													
Physical examination	X			X		X		X	X	X	X	X	X	
Weight	X											X	X	
Height	X													
Vital signs	X	P	P	P	P	P	P	P	X	X	X	X	X	
ECGs	X	P	P	P	P	P	P	P				X	X	

]	Part B: I	LY38723	886 CCI		De	osing Sch	nedule				
Procedures/ Assessments	Screening			Treat	tment Pe	eriod				Follo	w-up		ED	Comments
Visit Number	V1	V2	V3	V4	V5	V6	V7	V8	V	V	V	V		
									801	802	803	804		
Study Day(s)	CC													
Chest x-ray, if indicated (posterior-anterior view)	X													
IP administration		X	X	X	X	X	X	X						
QuantiFERON®-TB Gold test or TST	X													
vIGA-AD	X	X	X	X	X	X	X	X		X	X	X	X	
EASI	X	X	X	X	X	X	X	X		X	X	X	X	-
SCORAD	X	X	X	X	X	X	X	X		X	X	X	X	
POEM	X	X		X		X		X		X	X	X	X	
DLQI	X	X		X		X		X		X	X	X	X	
Itch numeric rating scale	X	X	X	X	X	X	X	X		X	X	X	X	
Laboratory Assessme	ents													
Beta-D-glucan	X													
Serologies, syphilis, and FSH	X													
Thyroid-stimulating hormone, including T3/T4 tests		P						X				X	X	
Serum immunoglobulins		X		X		X		X					X	

			I	Part B: I	LY38723	86 CC		Do	sing Sch	nedule				
Procedures/ Assessments	Screening			Treat	tment Pe	eriod				Follo	w-up		ED	Comments
Visit Number	V1	V2	V3	V4	V5	V6	V7	V8	V 801	V 802	V 803	V 804		
Study Day(s)	CC													
Subcutaneous local injection-site assessment		P	X	X	X	X	X	X		X	X	X	X	
Urinary drug screen (including ethanol breath test)	X	X	X	X	X	X	X	X						
Pregnancy test	X	P	P	P	P	P	P	P				X	X	
Clinical chemistry	X	X	X	X	X	X	X	X	X	X	X	X	X	
Fasting lipid panel		P		P		P			X				X	
Hematology	X	X	X	X	X	X	X	X	X	X	X	X	X	-
Hemoglobin A1c	X	X		X				X				X	X	
Urinalysis	X	X	X	X	X	X	X	X	X	X	X	X	X	-
Pharmacogenetics		P												-

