1.3.2.2. Part B: LY3872386 CC Dosing Schedule

1.3.2.2. Tared). L130/2			D. 4 D.			Scheut			.11.1.					
				Part B:	LY38/2	380		D D	osing S	cneauie				ı	T
Procedures/ Assessments	Screening		1	Treat	tment Pe	eriod				Fo	ollow-	up		E D	Comments
Visit Number	V1	V2	V3	V4	V5	V6	V 7	V8	V 801	V 802	V 803	V 804	V 805		
Study Day(s)	CC														
Informed consent	X														
Review/confirm I/E criteria	X	P													
IWRS randomization		P													
Clinical Assessments	•					'	1	•				1	'		
Complete medical history	X														
Review preexisting conditions/AEs	X	P	X	P	X	P	X	P		X	X	X	X	X	
Concomitant medications	X	P	X	P	X	P	X	P		X	X	X	X	X	
Previous and current AD treatments	X														
Substance use (alcohol and tobacco use)	X														
Physical examination	X			X		X		X			X		X	X	
Weight	X												X	X	
Height	X														
Vital signs	X	P	X	P	X	P	X	P		X	X	X	X	X	
ECGs	X	P		P		P		P					X	X	

				Part B:	LY3872	386 CC		D	osing S	chedule					
Procedures/ Assessments	Screening			Trea	tment Pe	eriod				Fo	ollow-	up		E D	Comments
Visit Number	V1	V2	V3	V4	V5	V6	V7	V8	V 801	V 802	V 803	V 804	V 805		
Study Day(s)	CC														
Chest x-ray, if indicated (posterior-anterior view)	X														
IP administration		X		X		X		X							
QuantiFERON®-TB Gold test or TST	X														
vIGA-AD	X	X	X	X	X	X	X	X		X	X	X	X	X	
EASI	X	X	X	X	X	X	X	X		X	X	X	X	X	
SCORAD	X	X	X	X	X	X	X	X		X	X	X	X	X	
POEM	X	X		X		X		X			X	X	X	X	
DLQI	X	X		X		X		X			X	X	X	X	
Itch numeric rating scale	X	X	X	X	X	X	X	X		X	X	X	X	X	
Laboratory Assessme	ents														
Beta-D-glucan	X														
Serologies, syphilis, and FSH	X														しし
Thyroid-stimulating hormone, including T3/T4 tests		Р						X					X	X	
Serum immunoglobulins		X		X		X		X							

				Part B:	LY3872	386 CC		D	osing S	chedule	2				
Procedures/ Assessments	Screening			Treat	tment Pe	eriod				Fo	ollow-	up		E D	Comments
Visit Number	V1	V2	V3	V4	V5	V6	V7	V8	V 801	V 802	V 803	V 804	V 805		
Study Day(s)	CC														
Subcutaneous local injection-site assessment		Р	X	X	X	X	X	X		X	X	X	X	X	See Section 8.2.6.
Urinary drug screen (including ethanol breath test)	X	X		X		X		X							
Pregnancy test	X	P		P		P		P					X	X	
Clinical chemistry	X	X	X	X		X	X	X			X	X	X	X	
Fasting lipid panel		P		P		P		P						X	-
Hematology	X	X	X	X		X		X			X	X	X	X	-
Hemoglobin A1c	X	X		X				X					X	X	_
Urinalysis	X	X	X	X		X		X			X	X	X	X	-
Pharmacogenetics		P													-
Immunogenicity		P	X	P	X	P	X	P		X	X	X	X	X	-

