- d Mean AUC value is inclusive of all animals, including 2 in which exposure was impacted by the presence of antidrug antibodies (see Section 4 of the IB). This value results in a more conservative estimate of exposure at the NOAEL.

Table KMAA.4. NOAEL-Based Dose and Model-Predicted Exposure Multiples for Proposed Repeat Administrations of LY3872386 to Human Participants

Abbreviations: AUC = area under the plasma concentration versus time curve; AUC_{0-336hr} = area under the plasma concentration versus time curve from time 0 to 336 hour (2 weeks); AUC_{0-672hr} = area under the plasma concentration versus time curve from time 0 to 672 hour (4 weeks); IV = intravenous; C_{av,ss} = average plasma concentration over the dosing interval, at steady state; N/A = not applicable; NOAEL = no-observed-adverse-effect level; CC

- a Calculations based on cookg patient.
- b Dose multiple is the dose in animals divided by the dose in humans based on mg/kg.
- c AUC value is expressed as average plasma concentration (C_{av,ss}) to normalize for differences in the dosing interval between studies in humans and monkeys, and is calculated by dividing the AUC value by the number of hours in the dosing interval.
- $^{
 m d}$ Monkey $C_{av,ss}$ /predicted human $C_{av,ss}$ is used to calculate a conservative estimate of exposure multiple.
- e NOAEL determined in a 3-month repeat-dose toxicity study (Study 20341655). C_{av,ss} is calculated from the AUC of CCI ng*hr/mL.

Prednisone Dose Justification:

Doses of \overline{CC} mg and sometimes up to \overline{CC} mg of prednisone are common in inflammatory diseases to treat acute flares for short durations (≤ 3 months).

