10.8. Appendix 8: Protocol Amendment History

The Protocol Amendment Summary of Changes Table for the current amendment is located directly before the Table of Contents.

Amendment a: 12 October 2023

Overall Rationale for the Amendment:

This protocol has been amended to correct previous errors in assessments and time points in the schedule of activities and to correct volume errors in the blood sampling summary. These changes are presented in the summary of changes table.

Minor editorial changes have also been made and are not presented in the summary of changes table.

Section # and Name	Description of Change	Brief Rationale
Section 1.3.1: Part A: Single-Ascending Dose of LY3872386 in Healthy Participants	Updated the vital signs assessment on Day 1 to indicate that it should not be predose only. Moved the thyroid-stimulating hormone, including T3/T4 test from screening to Day -1. Updated the cortisol assessment to no longer specify "basal," moved the test from screening to Day -1, and added a predose and 12-hour cortisol assessment to Day 1. Added a cosyntropin stimulation test to Day 15 ± 1d.	Corrections to previous errors.
Section 1.3.2: Part B: Multiple-Ascending Dose of LY3872386 in Patients with Atopic Dermatitis	Schedule: Moved the thyroid-stimulating hormone, including T3/T4 test from screening to predose on Day 1. CCI Dosing Schedule: Moved the thyroid-stimulating hormone, including T3/T4 test from screening to predose on Day 1.	Correction to previous error. Corrections to previous errors.

Section # and Name	Description of Change	Brief Rationale
	Updated the immunogenicity assessments on Day $15 \pm 1d$, Day $43 \pm 1d$, and Day $71 \pm 1d$ to indicate that it should not be predose.	
	Updated the LY3872386, total antibody, and LY3558533 concentration assessment on Day 15 \pm 1d, Day 43 \pm 1d, and Day 71 \pm 1d to indicate that it should not be predose.	
	Updated the receptor occupancy assessment on Day $15 \pm 1d$, Day $43 \pm 1d$, and Day $71 \pm 1d$ to indicate that it should not be predose.	
	Updated the cytokine panel assessment on Day $15 \pm 1d$, Day $43 \pm 1d$, and Day $71 \pm 1d$ to indicate that it should not be predose.	
	Updated the CCI assessment on Day 15 ±1d to indicate that it should not be predose.	
Section 1.3.3: Part C: Open- Label Multiple Dose of Prednisone in Healthy Participants	Prednisone — mg and — mg Dosing Schedule:	Corrections to previous errors.

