10.3 Pharmacokinetic Assessment

10.3.1 Pharmacokinetic Analysis

The following PK parameters will be determined using noncompartmental methods in validated software program Phoenix WinNonlin (Certara, Version 8.3.5 or higher):

Plasma concentrations of LY3872386, total antibody, LY3558533 (free payload) will be used to determine the following PK parameters for Parts A and part B, where possible:

CONFIDENTIAL Protocol Reference: J4L-MC-KMAA

For Part A - SAD (Cohorts 1 to 8):

Parameter	Units ^a	Definition
AUC(CCI)	μg.h/mL	area under the concentration versus time curve from time 0 to hours post dose.
AUC(CCI)	μg.h/mL	area under the concentration versus time curve from time 0 to hours post dose.
AUC _(0-t)	μg.h/mL	area under the concentration versus time curve from time 0 to the time of the last quantifiable concentration.
$\mathrm{AUC}_{(0-\infty)}$	μg.h/mL	area under the concentration versus time curve from time 0 to infinity
$\%AUC_{(tlast-\infty)}$	%	fraction of AUC(0-∞) extrapolated
C_{max}	$\mu g/mL$	maximum observed drug concentration
t_{max}	h	time of the maximum observed drug concentration
t _{1/2}	h	half-life associated with the terminal rate constant (λ_z) in non-compartmental analysis
CL/F	L/h	apparent total body clearance of drug calculated after extra-vascular administration (for LY3872386 only)
V _z /F	L	apparent total body clearance of drug calculated after extra-vascular administration (for LY3872386 only)
CL	L/h	total body clearance of drug calculated after intravenous administration (for LY3872386 only)
Vz	L	Volume of distribution during terminal phase (LY3872386 IV dosing)
F	%	bioavailability of drug. Fraction of extravascular dose reaching the general circulation compared to an IV administration

^a Units are based on concentration units (provided by the bioanalytical lab or preferred units for presentation of PK parameters) and dose units used in the study.

For Part B - MAD (Cohorts 1 and 2), Profile Day 1 and Day 85:

Parameter	Unitsa	Definition
AUC _(0-t)	μg.h/mL	area under the concentration versus time curve from time 0 to the time of the last quantifiable concentration. b
AUC_{τ}	μg.h/mL	area under the concentration versus time curve during one dosing interval
$\mathrm{AUC}_{(0-\infty)}$	μg.h/mL	area under the concentration versus time curve from time 0 to infinity ^b
$\%AUC_{(tlast-\infty)}$	%	fraction of AUC(0- ∞) extrapolated
C_{max}	$\mu g/mL$	maximum observed drug concentration

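### The Part B efficacy ANCOVA is planned at Weeks 1 and 12, but neither Part B schedule has a visit at Week 1, so one of its two time points has no scheduled data

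*SAP*

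**What the plan says.** SAP 10.7.2 plans an ANCOVA of mean percent change from baseline, with treatment as a fixed effect and 90% confidence intervals for the LS means. The endpoint name is blacked out. The time points are legible: the "data will be analyzed on Weeks 1 and 12 by an ANCOVA model with baseline as a covariate".

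Protocol 1.3.2.1 and 1.3.2.2 give the two Part B schedules, with one column per visit. In both, the treatment period is V2 to V8, with no column between V2 and V3 and only V3 between V2 and V4. For example, the "Itch numeric rating scale" row in 1.3.2.2 is marked at V2 and next at V3. The Study Day row is blacked out in both schedules, but other parts of the documents date most of the visits.

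SAP 6 says the biometrics and sponsor teams are unblinded for the whole study. Protocol 9.3.4.1 makes efficacy exploratory, with no hypothesis tests.

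**The concern.** An ANCOVA of change from baseline needs a post-baseline value at the stated time. If no visit is scheduled at Week 1, the only data there would come from an early-discontinuation or unscheduled visit that happened to fall near Day 8. That would not support a between-group model.

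The plan then either yields an empty output or invites a substitute early visit. Several substitutes exist, and the SAP does not say which applies. Because the analysis and sponsor teams see treatment assignments as data accrue, a visit chosen later could be chosen with the results in view.

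**Working it through.** No sample-size or power figure is involved. The check rebuilds the Part B calendar and asks whether a visit falls at each planned time point. Amendment entries are used only to date visits that remain in the current schedules.

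**Dates common to both schedules**

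- HbA1c is marked at V2, V4, V8 and the last follow-up visit. The amendment b table gives its post-screening days in Part B as 1, 29, 85 and 183. So V2 = Day 1, V4 = Day 29, V8 = Day 85.
- Ocular assessments after screening are marked at V4, V6, V801 and the last follow-up visit. Amendment b adds Days 29, 57 and 88 and notes that "for Visit 4, Visit 6, and follow-up Visit 801, an ocular pressure assessment is required". So V6 = Day 57 and V801 = Day 88.
- Serial PK sampling is marked at V2 and V8. SAP 10.3.1 sets the Part B profiles at "Profile Day 1 and Day 85", which agrees.
- Cross-check: Protocol 4.1 ends follow-up 14 weeks after the last dose. 85 + 14 × 7 = Day 183, as stated.

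**V3 in the second schedule (1.3.2.2): documented.** The amendment a entry in Protocol 10.8 begins "Updated the immunogenicity assessments on Day" and names Days 15, 43 and 71, each ± 1 day, as no longer predose. In the current table the non-predose immunogenicity marks within the treatment period are at V3, V5 and V7. So V3 = Day 15. Doses at V2, V4, V6 and V8 give (85 − 1)/3 = 28 days = 672 h.

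**V3 in the first schedule (1.3.2.1): inferred.** The "IP administration" row is marked at all seven visits V2 to V8, which makes six intervals: (85 − 1)/6 = 14 days = 336 h. The abbreviation list of Table KMAA.4 names both a 336-hour and a 672-hour interval. A 14-day step from Day 1 reproduces every anchor:

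| Visit | V2 | V3 | V4 | V5 | V6 | V7 | V8 |
|---|---|---|---|---|---|---|---|
| Day | 1 | 15 | 29 | 43 | 57 | 71 | 85 |
| Anchor | 1 | – | 29 | – | 57 | – | 85 |

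Putting V3 at Day 8 instead would make the first two dosing gaps 7 days (168 h) and 21 days (504 h). Nothing in the documents supports that.

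**Week 1 and Week 12 under either numbering**

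- Week n = Day 7n + 1: Week 12 = Day 85 = V8, a scheduled visit. Week 1 = Day 8, no visit. Distance to nominal V3: 15 − 8 = 7 days; to the early edge of a ± 1 day window: 14 − 8 = 6 days.
- Week n = Days 7n − 6 to 7n: Week 1 = Days 1 to 7, which contains only V2, the baseline. Week 12 = Days 78 to 84, which contains no nominal visit (V7 = 71, V8 = 85).

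Only the first numbering makes Week 12 work, and neither gives a post-baseline Week 1 value.

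**Scheduled visits that could stand in, before Week 12**

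- EASI, vIGA-AD, SCORAD, itch: V3 to V7, that is 5 visits (Weeks 2, 4, 6, 8, 10).
- POEM, DLQI: V4 and V6, that is 2 visits (Weeks 4, 8).

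**The case against.** The strongest opposing points, and what is left of each:

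- **The SAP already handles empty outputs.** SAP 14.3 prints a blank shell with a message when data are insufficient, and SAP 3 requires substantial deviations to be agreed with the sponsor and identified in the CSR. So no one is forced to choose a substitute. This stands, and it softens the worry about a late choice. It also confirms that the plan as written gives nothing at Week 1.
- **Redactions could hide a Week 1 collection.** The endpoint, the Study Day rows and much of Protocol 8.1 are not visible, so a between-visit collection of a participant-rated scale cannot be strictly ruled out. But the legible text in 8.1 ties the participant-rated assessments to study-visit days, and what is missing is a visit column, so the identity of the endpoint does not matter.
- **Day 15 in the first schedule is inferred.** True. Equal spacing is an assumption, and Part B dosing frequency is still to be confirmed (Protocol 1.1, SAP 7). The anchors leave little room for another reading.
- **The SAP was written from the protocol of 01 September 2023, which is not among the documents.** An earlier schedule may have differed. The amendment tables list no removed Part B visit, and if one was removed, the SAP is out of date and still conflicts with the current schedule.
- **Intent is unknown.** Week 1 may be a slip for another week. This stands and bears on the fix: the sponsor must say what was meant.

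**Conclusion.** The concern holds. Of two planned ANCOVA time points, one has a scheduled post-baseline visit. No Part B visit is scheduled between Day 1 and V3. This is documented for the second schedule. For the first it rests on equal dosing intervals between the dated visits.

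The consequence is modest. It affects one time point of an exploratory Part B model. Week 12, the descriptive efficacy summaries, the primary safety analysis and the secondary PK analysis are untouched. It should be corrected because a stated analysis cannot be carried out as written, and because the teams who would choose a replacement are unblinded.

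**What to change.** Before unblinded efficacy data are reviewed, settle what Week 1 was meant to be and amend SAP 10.7.2 accordingly.

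- **If an early scheduled visit was meant:** replace Week 1 with a visit at which the analysed endpoint is collected, named by study day. The nearest is Week 2 (V3, Day 15) for EASI, vIGA-AD, SCORAD or itch, and Week 4 (V4, Day 29) for POEM or DLQI. The cost is one SAP phrase and the matching TFL shell, with no new data or visits. The drawback is a later first reading than Week 1.
- **If a true Week 1 reading was meant:** reconcile the SAP with the schedule of activities. That needs a protocol change and an extra visit in both Part B schedules.

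Keep Week 12 as it is. Protocol 8 allows time points to be modified on emerging information, so if the Part B frequency or visit days change, restate the analysis visit by study day.
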